7.2 Study Population

7.2.1 Disposition of Subjects

The following subject data will be summarized overall and by treatment group. Unless otherwise noted, the data will be summarized using the randomized treatment group:

- Number of subjects who provided informed consent, who discontinued before randomization, who were randomized, who received a transplant, and who had at least one post-baseline assessment;
- Number and percentage of subjects in each analysis set;
- Number and percentage of subjects who discontinued (actual) tacrolimus treatment for any reason, with primary reason for treatment discontinuation presented; and
- Number and percentage of subjects excluded from the PPS by reason for exclusion.

A subject listing for early discontinuations and reasons for discontinuation will be provided.

7.2.2 Protocol Deviations

Protocol deviations as defined in the study protocol (Section 8.1.6 Protocol Deviations) will be assessed for all randomized subjects. The number and percentage of subjects with major protocol deviations will be summarized by criterion, (randomized) treatment group, and overall. Protocol deviations will also be summarized by study site. Subjects with more than one major deviation from the same criterion will be summarized once for the corresponding criterion. Any subjects who have more than one major deviation will be counted once in the overall summary. A data listing will be provided for all deviations by site and subject.

All deviations will be assessed as either major or minor according to a final review meeting prior to unblinding.

The protocol deviation criteria will be uniquely identified in the summary table and listing. The unique identifiers will be as follows:

- PD1 - Entered into the study even though they did not satisfy entry criteria,
- PD2 - Developed withdrawal criteria during the study and was not withdrawn,
- PD3 - Received wrong treatment or incorrect dose,
- PD4 - Received excluded concomitant treatment.

7.2.3 Demographic and Other Baseline Characteristics

Demographic and other baseline characteristics will be summarized using descriptive statistics, presented overall and by randomized treatment group.

Number and percentage of subjects randomized in each site will be presented by treatment group for the SAF.

7.2.3.1 Recipient Demographics

Descriptive statistics for age (years), age categories (≤ 17 , 19-34, 35-49, ≥ 50), weight (kg), body mass index (BMI, kg/m^2) and height (cm) will be presented. Frequency tabulations for sex, ethnicity, age group (defined in section 7.8) and race will be presented. This will be done for the non-randomized subjects, as well as for the SAF, FAS, mFAS, PPS, and BAS by treatment group. A listing of demographic characteristics will also be provided.

7.2.3.2 Donor Demographics and Baseline Characteristics

Descriptive statistics for donor demographic and baseline characteristics of age (years), weight (kg), height (cm), BMI (kg/m^2), KDPI will be presented. Frequency tabulations for age groups (≤ 17 , 18-34, 35-49, ≥ 50), extended criteria donor (ECD), race, ethnicity, Living/Deceased donor, deceased donor type, cause of death of deceased donor, Donation after Circulatory Death (DCD), will be presented. This will be done for the FAS, mFAS, SAF, PPS, and BAS by treatment group. A listing of demographic characteristics will also be provided.

7.2.3.3 Recipient Baseline Disease Characteristics

Baseline characteristics, including primary etiology of end of stage renal disease (ESRD), duration of ESRD prior to transplantation (months), on dialysis prior to current transplant, duration of dialysis prior to transplant, type of dialysis, weight before transplant, and reason for dialysis will be summarized using the FAS by treatment group.

7.2.3.4 Baseline Viral Serology

The number and percent of subjects for each recipient/donor pair with the following results at baseline: (Positive – Positive, Positive – Negative, Negative – Positive, Negative – Negative)

for viral serology test Hepatitis B Core Antibody IgG and Hepatitis C Antibody will be summarized using the FAS by treatment group.

All baseline viral serology data will be listed.

7.2.3.5 Transplant Related Information

The following transplant-related information will be summarized using the FAS by treatment group:

- Number and percent of previous kidney transplants
- Reason for most recent graft loss
- Type of transplant
- ABO compatibility for each recipient/donor pair
- Calculated Panel reactive antibody (cPRA)
- Organ storage method
- Any complications in organ preservation or transplant procedure?
- Cold ischemic time
- Warm ischemic time
- Test used for recipient histocompatibility
- Crossmatch results
- Pre-transplant donor kidney biopsy performed (yes/no)

7.2.3.6 DSA Testing

The following transplant-related information will be summarized using the FAS by treatment group:

- Method used
- Any evidence of DSA positivity
- Single Antigen Bead Testing performed

7.2.3.7 Medical History

Targeted diabetes medical history and non-diabetic medical history will be collected. The number and percent of subjects with each targeted diabetes medical history condition will be summarized using the SAF by treatment group. All non-diabetic medical history conditions are coded in MedDRA version 20.1, and will be summarized by System Organ Class (SOC) and Preferred Term (PT) as well as by PT alone, by treatment group for the SAF. All medical history data will be listed.

7.2.4 Previous and Concomitant Medications

Previous medications will be coded using the version September 2017 of the World Health Organization Drug Dictionary (WHO-DD), and will be included in data listings.

Concomitant medications will be summarized for each treatment group by therapeutic subgroup (ATC 2nd level) and chemical subgroup (ATC 4th level) for the SAF. Subjects taking the same medication multiple times will be counted once per medication.

Immunosuppression medications including mycophenolic acid (MMF, EC-MPS, or generic total daily dose [mg]), corticosteroids usage (total daily dose [mg]), and antithymocyte globulin (total daily dose [mg]) will be summarized.

Separate listings for concomitant and immunosuppression medications will be provided.

7.3 Study Drugs

7.3.1 Exposure

The following information on drug exposure according to the details in Section 6.5 will be presented for each treatment group for the SAF:

- Descriptive statistics for cumulative amount of the drug that a subject was exposed to and average daily dose; and
- Number and percent of subjects with dose increases, decreases, or interruption by treatment group.

Duration of exposure will be summarized in two ways.

- Descriptive statistics will be presented by treatment group.
- Exposure time will be categorized according to the following categories by treatment group:
 - less than 7 days
 - at least 7 days, less than 14 days
 - at least 14 days, less than 28 days
 - at least 28 days, less than 42 days
 - at least 42 days, less than 60 days
 - at least 60 days, less than 91 days
 - at least 91 days, less than 182 days
 - at least 182 days, less than 364 days
 - 364 days or more
 - Unknown.

Counts and percentages of subjects in each of these categories will be summarized for each treatment group for the SAF.

Additionally, descriptive statistics (counts and percentages) will be used to assess for the BID Immediate-release Tacrolimus treatment group for the SAF the distribution of use for the different tacrolimus formulations in the study (i.e., generic formulations of immediate release tacrolimus) and the frequency of manufacturer switching for the study.

7.3.2 Treatment Compliance

Treatment Compliance is only available for the BID Immediate-release tacrolimus treatment group. See section 6.5. All analyses planned in the Protocol to compare compliance between treatment groups will not be conducted.

PDC, MPR rates and their compliance values will be descriptively summarized for the BID Immediate-release Tacrolimus treatment group.

7.3.3 Tacrolimus Trough Concentrations

Since tacrolimus trough concentration is not assessed at scheduled visits and each subject may have different numbers of assessments. Following analyses will be conducted:

- 1) Based on all tacrolimus trough concentration assessments from D30 to Day 365, the number of assessments, the mean and median trough level of each subject will be calculated and summarized by treatment group.
- 2) Number of excursions of tacrolimus trough concentrations above 120% or below 80% of the average trough level of each subject will be tabulated as a proportion of the all tacrolimus trough concentrations reported during the study: proportion of tacrolimus trough concentrations above 120% or below 80% of the average trough level = $100 \times (\text{number of tacrolimus trough concentrations above 120\% or below 80\% of the average trough level} / \text{total number of tacrolimus trough concentrations})$.
- 3) IPV estimated from CV, geometric CV, and SD, and Dose-adjusted IPV_s (see section 6.5) will be summarized by treatment group. The summaries will be provided for SAF and subgroups of subjects with TG, microcirculatory inflammation, or BPAR.
- 4) IPV_s will also be visually presented in Box plots.

Mean tacrolimus level, number of excursions of tacrolimus trough concentrations above 120% or below 80% of the average trough level, and IPV estimated by CV% will also be used as covariates in the risk factor analysis. See section 7.4.2.

IPV_s will also be estimated from the mixed model and functional regression model (Kim et al., 2019). The methods and results will be presented in a separate report, and are not covered by this SAP.

7.4 Analysis of Efficacy

The analysis of Efficacy will be conducted using the mFAS, with sensitivity analyses using the FAS and PPS. All efficacy analyses related to central pathology findings will be conducted using BAS. Risk factor analysis will be conducted for both mFAS and PPS.

7.4.1 Analysis of Primary Endpoint(s)

7.4.1.1 Primary Analysis of Primary Endpoint

The primary analysis will be performed on the primary composite endpoint of combined incidence of either De Novo DSA or IA on molecular blood profiling at one year. Both De novo DSA (Positive/Negative) and IA (Present/Absent) will be considered binary. DSA positivity is assessed by the Transplant Immunology Lab of Northwestern University.

In the case where MFI signal is greater than 1000, and DSA is suspected, but the formation of De Novo DSA cannot be confirmed due to inadequate donor typing, the formation of De Novo DSA will be labeled indeterminate. If subject discontinues the study between D0 and D30, and no testing results are available, then De Novo DSA will be assumed to be negative. If subject does not have a specimen collection, then De Novo DSA will be assumed missing and will be excluded from primary efficacy analysis, but will be assumed to be negative in

sensitivity analysis. The table below shows the logic set up for actual assessment of study composite endpoint.

De Novo DSA	IA	Study Composite Endpoint
Positive	Present	Positive
Positive	Not Present	Positive
Positive	Unknown	Positive
Negative	Present	Positive
Negative	Not Present	Negative
Negative	Unknown	Indeterminate
Indeterminate	Present	Positive
Indeterminate	Not Present	Indeterminate
Indeterminate	Unknown	Indeterminate

The proportion of subjects meeting the primary composite endpoint definition will be summarized by treatment group. The difference in the proportion of subjects meeting the primary composite endpoint definition and 95% confidence interval will also be provided.

The primary analysis of the treatment group comparison will be based on fitting a multivariable binary logistic regression model with randomized treatment group (Astagraf XL group versus twice-daily, immediate-release tacrolimus group), pre-defined randomization stratification factors (planned use of Campath [Yes/No], levels of KDPI as defined in Section 4.5 of the protocol, and HLA Class II mismatch), recipient age, gender, and race, and pre-transplant cPRA included in the model. Investigational site will be included as a random effect. The limited numbers of subjects per center, however, may make it impracticable to include all sites in the statistical model. If reasonable, data from low enrolling sites (e.g., < 5 subjects) will be combined. The decision to include sites and how to combine sites, if necessary, will be made prior to database unblinding.

Adjusted (common) odds ratio (OR: Astagraf XL group versus immediate-release tacrolimus group) and two-sided exact 95% CI will be provided as measures of strength of association and precision, respectively. The null hypothesis of no treatment effect can be expressed as $H_0: OR = 1$ and will be tested at the ≤ 0.05 level using the Wald's chi-square statistic on one degree of freedom. Odds ratio will also be estimated for the covariates included in the model.

Subjects with primary endpoint unknown, undetermined, or missing will be excluded from the primary analysis.

The hypothesis for the comparison is as follows:

H₀: The proportion of subjects with the primary endpoint is the same between subjects receiving Astagraf XL and subjects receiving immediate-release tacrolimus.

H₁: The proportion of subjects with the primary endpoint is not the same between subjects receiving Astagraf XL and those receiving immediate-release tacrolimus.

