6. HLA-DQ DSA
7. DSA IgG₃ isotype
8. Requirement for antibody reduction therapy
9. eGFR at various thresholds (less than 30, 40, 50 mL/min/1.73 m² at one year or later; and a five-point decline)
10. Graft loss (defined as subject death, retransplantation, transplant nephrectomy, or a return to dialysis for at least a 6 week duration)
11. Mortality
12. BPAR (inclusive of ABMR and TCMR)
13. The four-part traditional composite endpoint: graft loss, local BPAR, mortality, and lost to follow-up (note – lost to follow-up will be summarized descriptively only)

GEE models used for analysis of treatment group differences will use the same covariates detailed in Section 7.4.1.1 with the exception of biopsy-based endpoints (i.e., TG and ABMR). In addition to the set of covariates from Section 7.4.1.1 biopsy-based endpoints will also include the covariates of CIT, WIT, KDPI, DCD status, and the three ex vivo perfusion parameters recorded pre-transplant. Similar to the primary endpoint, additional changes/details for the set of covariates will be included in the SAP.

For study purposes, lost to follow-up is defined as a subject failing to complete their final study visit no more than 30 days prior to the scheduled visit, and without a prior incidence of local BPAR, graft loss, or death. The incidence of lost to follow-up will be summarized with frequencies and percentage by treatment group.

The assessments of time to first occurrence for DSA, HLA-DQ DSA, C1q-binding DSA, DSA IgG₃ isotype, IA, TG, select BANFF histology grades (acute and chronic forms of ABMR, acute and chronic active TCMR, borderline changes, and IFTA), graft loss, mortality, local BPAR, and the four-part traditional composite endpoint will be summarized from the date of transplant. For patients who did not experience the endpoint event and/or were lost to follow-up or died prior to reporting the event, they will be censored at the date of their last known assessment/follow-up/death. Summaries will include estimable quartiles of time-to-first event with 95% confidence interval, Kaplan-Meier (KM) figures, and hazard ratios with 95% confidence interval. In the event that the median times are not estimable, the proportion of subjects with no DSA formation at the one and two year time points (as applicable) will be summarized by treatment group. Treatment group differences will be assessed with Cox regression models that account for the same covariates as used in the analogous GEE models.

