These threshold endpoints will be calculated for months 1, 3, 6, 9, and 12 using the Modification of Diet in Renal Disease (four variable-MDRD) criteria. Assessments are positive or negative.

- Five-point decline in eGFR

The decline in eGFR will be calculated with respect to the eGFR value at Day 30 visit.

- Traditional transplantation composite endpoint

Incidence will be assessed at month 12 for the following:

- Graft loss (defined as retransplantation, transplant nephrectomy, or a return to dialysis for at least a six week duration, or subject death)
- Death
- BPAR – positivity will be determined by local biopsy, central pathology, or reported adverse events.
- Composite occurrence of either graft loss, death, BPAR, and loss-to-follow-up

- Histopathology grading within 1 year

Central histopathology grading over 1 year will be diagnosed according to the BANFF diagnostic categories and subcategories that include the following:

- Normal
- Antibody mediated changes
 - C4d deposition without morphologic evidence of active rejection
 - Acute ABMR (grades: I, II, and III)
 - Chronic active ABMR
 - ABMR: either Acute ABMR or Chronic Active ABMR
- Borderline changes
- TCMR
 - Acute TCMR (grades: IA, IB, IIA, IIB, and III)
 - Chronic active TCMR
- IFTA (grades: I, II, and III)
- Other: all categorical findings will be summarized.
- In addition to the categories above, specimens will be given individual scores for the following: glomerulitis (g), tubulitis (t), intimal arteritis (v), mononuclear cell interstitial inflammation (i), early allograft Glomerulopathy (cg), tubular atrophy (ct), interstitial fibrosis (ci), vascular fibrous intimal thickening (cv), arteriolar hyaline thickening (ah), peritubular capillaries (ptc) and mesangial matrix (mm).

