7.4.2 Analysis of Secondary Endpoints

Risk factor analysis will be conducted in two parts. First, is to identify risk factors for outcomes based on factors measured at time of transplantation (baseline) including the pre-defined stratification factors. Last, is to identify risk factors for outcomes based on factors that are measured post-randomization and therefore, are subject to change e.g., average daily dose of MPA treatment or cumulative dose of corticosteroids. All models will include randomized treatment, irrespective of statistical significance. Models to assess risk factors for binary or categorical variables will be done using logistic regression. Odds ratio and 95% CI will be used as measures of strength of association and precision, respectively.

Risk factor analyses will be conducted for eight binary variables: IFTA, IFTA and Inflammation, BPAR, the four-part traditional composite endpoint, early MMF interruption/discontinuation, and eGFR status based on three thresholds 30, 40, and 50. The biopsy data are based on the central pathology results over the course of one year plus 2 months window. eGFR status variables are based on the assessment at Day 365 visit.

Each risk factor analysis model will include treatment group and a main factor: either De novo DSA, IA, or the composite of De novo DSA and IA. Following additional covariates will be considered for the two types of models, and a multicollinearity assessment will be proceeded for the final variable selection:

Risk factors measured at time of transplantation include:

- Cold ischemic time
- Warm ischemic time

- KDPI% \leq 50% (yes/no)
- KDPI% $>$ 50% (yes/no)
- HLA Class II mismatch (yes/no)
- Donor status (living/deceased)
- Donation after circulatory death (yes/no)
- Donor Age
- Donor-Recipient sex mismatch (match/mismatch)
- Donor-Recipient race mismatch (match/mismatch)
- Preservation by cold storage (yes/no)

Post randomization risk factors include:

- Cumulative Dose of Corticosteroids
- Average daily dose of MPA
- Mean dose level of tacrolimus
- Mean tacrolimus trough level
- Number of excursions below 80% or above 120% of the average tacrolimus trough level
- IPV estimated by CV%
- Post-transplant BK virus infection

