7.10 Handling of Missing Data, Outliers, Visit Windows, and Other Information

7.10.1 Missing Data

Generally, all missing efficacy endpoints (e.g. DSA, IA, pathological findings, eGFR) will not be imputed. Only for the sensitivity analyses, e.g. the sensitivity analysis of primary endpoint (section 7.4.1.2), the indetermined endpoint will be imputed as Negative.

In AE summary tables, the missing AE severity and relationship to study drug will be replaced with the highest level of severity and relationship: “Severe” and “Probable”, respectively. In AE data listing, original missing data will be displayed.

As a general principle, no imputation of missing data for other variables will be done.

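### SAP 7.4.1.1 scores a D0–D30 leaver with no test as de novo DSA-negative, against its next sentence and SAP 7.10.1. The primary composite is untouched, but a secondary DSA odds ratio can be biased downward.

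*SAP*

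**What the plan says.** SAP 7.4.1.1 has two adjacent rules for absent DSA data.

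- For a subject who discontinues between D0 and D30: "no testing results are available, then De Novo DSA will be assumed to be negative".
- In the next sentence: "If subject does not have a specimen collection, then De Novo DSA will be assumed missing and will be excluded from primary efficacy analysis". Such a subject is set to negative only in sensitivity analysis.

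SAP 7.10.1 gives the general rule: "Generally, all missing efficacy endpoints (e.g. DSA, IA, pathological findings, eGFR) will not be imputed". Its exception is "Only for the sensitivity analyses, e.g. the sensitivity analysis of primary endpoint (section 7.4.1.2), the indetermined endpoint will be imputed as Negative".

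De novo DSA is used again in SAP 7.4.2. It is the first secondary endpoint compared between arms, and it is a predictor: "Each risk factor analysis model will include treatment group and a main factor: either De novo DSA, IA, or the composite". One of the eight risk-factor outcomes is the four-part composite, defined in SAP 6.1.2 as "Composite occurrence of either graft loss, death, BPAR, and loss-to-follow-up". The SAP does not say what counts as loss to follow-up. Protocol 7.4.2 does: "lost to follow-up is defined as a subject failing to complete their final study visit", provided there was no earlier local BPAR, graft loss or death.

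**The concern.** The first post-transplant DSA sample is due at Day 30 (±21 days). Most subjects who leave before Day 30 without a result therefore also have no specimen, so both sentences apply and give opposite codes. A programmer has to choose.

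If negative is chosen, subjects who were never tested are counted as tested and clear. As an outcome, that dilutes the DSA rate. As a predictor of the four-part composite, it matters more, because an early leaver either had BPAR, graft loss or death, or failed to complete the final visit. Protocol 6.1 collects nothing further after discontinuation beyond adverse-event information. Under the protocol definition, nearly every such subject is then a DSA-negative event by construction, and the association of DSA with outcome is pulled downward.

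The models for one outcome would also rest on different subjects. Untested leavers stay in when DSA is the main factor, but they are unknown or indeterminate when IA or the composite is.

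**Working it through.** **1. Base.** The documents do not give the number of untested early leavers. The one related figure is enrolment: 220/(1 − 0.20) = 275 per group, 550 in total, as stated in SAP section 4. That figure reproduces and is not in question.

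**2. Primary composite.** In the SAP 7.4.1.1 table, DSA negative with IA unknown is indeterminate, and the same section excludes undetermined endpoints. An untested leaver has no IA result either, so the rule changes nothing here.

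**3. Which SAP 7.4.2 analyses keep these subjects.** The mFAS requires randomization, one dose and no pre-formed DSA. It does not require a post-transplant test.

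| Analysis | Early untested leavers |
|---|---|
| De novo DSA incidence (item 1) | Kept, as negatives |
| eGFR thresholds at Day 365 | Drop out, no value |
| IFTA; IFTA and inflammation (central pathology, BAS) | Mostly drop out, need a biopsy |
| Post-randomization models with trough mean (Day 30–365) or IPV (after Day 42) | Drop out if those covariates are kept |
| Time-of-transplant model, four-part composite | Kept, DSA-negative and nearly all events |
| Time-of-transplant models, BPAR and early MMF interruption | Kept, but event status is not fixed by definition |

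**4. DSA incidence.** Observed rate = tested rate × (1 − untested share). With 10% among those tested, 2% untested gives 0.10 × 0.98 = 9.8%, and 6% untested gives 0.10 × 0.94 = 9.4%. If the arms differed by that much in early leaving, equal true rates would read 9.8% and 9.4%.

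**5. Four-part composite model.** Assumptions: N = 550, 10% DSA-positive among tested subjects, composite rate c = 20% in tested DSA-negatives (odds 0.25), and k untested leavers, all events. Adding k to the DSA-negative event cell gives odds (n_neg·c + k)/(n_neg·(1 − c)). The DSA-positive odds do not move. So

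OR_observed = OR_true / (1 + k/(n_neg·c)).

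| Untested | k | Tested | n_neg | n_neg·c | Divisor | True 1.0 reads | True 2.0 reads |
|---|---|---|---|---|---|---|---|
| 1% | 5.5 | 544.5 | 490.05 | 98.01 | 1.056 | 0.95 | 1.89 |
| 3% | 16.5 | 533.5 | 480.15 | 96.03 | 1.172 | 0.85 | 1.71 |
| 5% | 27.5 | 522.5 | 470.25 | 94.05 | 1.292 | 0.77 | 1.55 |

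This is unadjusted 2×2 algebra. The planned model is adjusted, so these figures show direction and rough size.

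**6. How many leavers would bring the odds ratio down to 1.** Set OR_observed = 1 and A = c·(OR − 1)·0.9. Then k = 550·A/(1 + A). With c = 20%, a true 1.5 needs A = 0.09 and k = 45 (8.3%). A true 2.0 needs A = 0.18 and k = 84 (15.3%). Varying c from 15% to 25% gives 35–56 and 65–101.

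**7. If not all leavers are events.** Let a share q be events, so the DSA-negative odds become (n_neg·c + q·k)/(n_neg·(1 − c) + (1 − q)·k). With c = 15% and k = 20, a true 1.0 reads 0.78 at q = 1 and 0.90 at q = 0.5. The pull vanishes when q falls to c.

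**The case against.** - **Carry-over to SAP 7.4.2 is inferred.** The sentence sits in the primary-endpoint section. SAP 6.1.2 bases DSA occurrence on the visit assessments, and SAP 7.10.1 says missing DSA is generally not imputed. This stands, so the effect is conditional. But the SAP gives no other derivation of the variable, and the two sentences would still conflict.
- **The early-leaver sentence may be a specific rule and the next one may cover everyone else.** That is a possible reading. Two subjects with the same absence of data would then be coded differently by departure date, and SAP 7.10.1 would still confine negative imputation to sensitivity analyses. Protocol 7.4.1.1 planned negative imputation in the primary analysis, so the sentence may be a remnant of that plan.
- **The event share depends on the loss-to-follow-up definition.** Protocol 6.1 also lists loss to follow-up as one discontinuation reason among many. If the SAP means only that category, many early leavers are not composite events and the bias shrinks. This stands.
- **The between-arm effect on DSA is negligible.** Agreed. At 10% prevalence with 2–6% untested there are about 52–54 positives, under the 57-subject floor in SAP 7.1. The DSA treatment regression would then not be run, and only the descriptive rate would be affected.
- **The base of 550 is generous.** The mFAS omits subjects who were never dosed or who had pre-formed DSA, some of whom leave early. This stands.
- **The fix does not yield a causal odds ratio.** A subject with one negative test who is then lost still counts as a DSA-negative event. This is true. Here, the true odds ratio means the one among tested subjects.

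**Conclusion.** The concern holds in limited form. A stated rule codes never-tested subjects as DSA-negative, against the next sentence and SAP 7.10.1. Its material effect is on the time-of-transplant model relating DSA to the four-part composite. There, with 1–5% untested early leavers and the assumptions above, the odds ratio is lowered by a factor of about 0.95 to 0.77. The effect on DSA incidence is a few tenths of a percentage point.

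A reader might infer three stronger things that the documents do not support.

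- **That the primary result is biased.** It is not, because these subjects are excluded as indeterminate.
- **That DSA will look protective.** The odds ratio passes below 1 only if the true association is null or weak, or if early untested leavers are many. In the range shown, a true 2.0 is attenuated and not reversed.
- **That every model with DSA as main factor is affected.** The eGFR, central-pathology and post-randomization trough models largely lose these subjects.

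The size rests on assumed values for the early-leaver share, DSA prevalence and composite rate, on the protocol's loss-to-follow-up definition, and on the variable carrying over unchanged.

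**What to change.** - Delete the D0–D30 sentence in SAP 7.4.1.1, or move it to the sensitivity analysis in SAP 7.4.1.2, which already imputes negatives.
- State that de novo DSA is missing for any subject with no post-transplant DSA result, whenever the subject left.
- Limit item 1 of SAP 7.4.2 and the models with de novo DSA as main factor to subjects with at least one post-transplant DSA result.

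The cost is one sentence, one derivation change, and a few untested subjects leaving the DSA analyses. The primary analysis and the sample size do not change.

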7.4.1 Analysis of Primary Endpoint

7.4.1.1 Primary Analysis

The primary efficacy endpoint is the combined incidence of either DSA or IA on molecular blood profiling at one year or at the conclusion of the study.

The primary endpoint will be analyzed at a single time point, corresponding to end of study and with respect to the formal stopping rule (see Section [7.8.1](#)). The primary analysis of this endpoint will be based on the mFAS. The incidence of the primary endpoint will be summarized by treatment group with frequencies and percentages. Differences between treatment groups will be analyzed using logistic regression with the following covariates: treatment group (Astagraf XL group versus the immediate-release group), the pre-defined randomization stratification factors, recipient age, race, and gender; type of induction therapy, delayed graft function, and pre-transplant cPRA.

For subjects with missing or incomplete endpoint data who did not permanently switch therapy or were discontinued from the study prior to a DSA/IA event, who are lost to follow up, or those who expire for any reason), negative DSA/ IA values will be imputed unless there is an otherwise positive result.

The hypothesis for comparison is as follows:

H0: The probability of incidence for the primary endpoint is the same between patients receiving Astagraf XL and patients receiving immediate-release tacrolimus.

H1: The probability of incidence for the primary endpoint is not the same between patients receiving Astagraf XL and those receiving immediate-release tacrolimus.

Hypothesis testing will be performed using a two-sided test with a 0.05 significance level. The 95% confidence interval for the odds ratio of the primary endpoint between Astagraf XL and twice daily tacrolimus will be included.

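### The SAP asks for an exact 95% CI on an odds ratio from a random-site logistic model, which has no standard exact interval; the interval should come from the same fit as the Wald test.

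*SAP*

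**What the plan says.** SAP 7.4.1.1 (Primary Analysis of Primary Endpoint) describes a single model: "The primary analysis of the treatment group comparison will be based on fitting a multivariable binary logistic regression model with randomized treatment group", the three stratification factors, and "recipient age, gender, and race, and pre-transplant cPRA included in the model". It adds: "Investigational site will be included as a random effect". It warns that small centres "may make it impracticable to include all sites in the statistical model" and leaves the pooling of sites to be settled before unblinding.

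Three results are then taken from the model:

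- the adjusted odds ratio;
- its interval: "two-sided exact 95% CI will be provided as measures of strength of association and precision";
- the hypothesis test, where an odds ratio of 1 "will be tested at the ≤ 0.05 level using the Wald's chi-square statistic on one degree of freedom".

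The SAP does not define *exact*, and its general considerations (7.1) name SAS 9.4 but no procedure. Protocol 7.4.1.1 is less specific: "The 95% confidence interval for the odds ratio of the primary endpoint between Astagraf XL and twice daily tacrolimus will be included". It does not ask for an exact interval and has no site effect. SAP 7.4.1.2 reuses the logistic analysis of 7.4.1.1 for the FAS and PPS. SAP 7.4.2 asks for an ordinary 95% CI in its risk-factor models.

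**The concern.** The interval and the model do not belong together. Exact logistic inference removes nuisance parameters by conditioning on their sufficient statistics. A random-site model integrates the site effect out of the likelihood, so there is no such conditional distribution for the treatment odds ratio. Its usual intervals are Wald, t or profile-likelihood intervals. The programmer must therefore either ignore the word exact or take the interval from another model, for example an unadjusted table or a model with site dropped or used as fixed strata.

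In the second case the headline line of the report would combine an odds ratio and p-value from one model with an interval from another. Near p = 0.05 a significant test could stand beside an interval that covers 1. The reader would not know that two models were involved, and the SAP does not say how to present the result.

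**Working it through.** **1. Inputs.** The SAP's sample size section (Section 4) and Protocol 7.1 give 20% versus 10%, 80% power, two-sided alpha 0.05, 220 per group, and 275 per group after 20% dropout. SAP 7.4.1.1 gives the model, the interval and the test.

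**2. The plan's own figure.** The pooled-variance formula is

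n = [1.96·√(2·0.15·0.85) + 0.8416·√(0.2·0.8 + 0.1·0.9)]² / 0.10² = (0.990 + 0.421)² / 0.01, which rounds up to 199.

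With the continuity correction, n′ = (n/4)·[1 + √(1 + 4/(n·0.10))]² gives 219, in line with 220. Fisher's exact test at 220 per arm has 81.1% power. Dropout: 220/0.8 = 275. The sample size reproduces and is not in question.

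**3. Is there an exact interval for this model?** Set side by side, the SAP asks for (a) a random site effect, (b) an exact interval and (c) a Wald test. Items (a) and (c) are compatible; (a) and (b) are not, for the reason given above. Conditioning on site as a stratum would give an exact analysis, but of a different, fixed-strata model. The random effect alone settles this, whatever form the covariates take.

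**4. How far apart can the two results be?** The documents do not allow this to be computed for the adjusted mixed model. The following is an unadjusted 2×2 illustration, with 28/220 events on Astagraf XL and 44/220 on control.

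- OR = (28·176)/(192·44) = 4928/8448 = 0.583, so ln OR = −0.539.
- SE = √(1/28 + 1/192 + 1/44 + 1/176) = √0.0693 = 0.263.
- Wald z = 0.539/0.263 = 2.05, p = 0.041; 95% CI exp(−0.539 ± 1.96·0.263) = 0.348 to 0.977, which excludes 1.
- Exact: the one-sided hypergeometric tail P(X ≤ 28), given 72 events in 440, doubled, is 0.053. The central exact 95% CI is 0.335 to 1.006, which includes 1.

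**5. How often?** All 2×2 tables were enumerated with binomial weights. A conflict is Wald p ≤ 0.05 with a central exact 95% CI that includes 1.

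| Per arm | Rates (control vs XL) | Wald significant | Exact CI excludes 1 | Conflict |
|---|---|---|---|---|
| 220 | 20% vs 10% | 84.0% | 81.1% | 2.9% |
| 275 | 20% vs 10% | 91.2% | 89.4% | 1.8% |
| 220 | 20% vs 20% (null) | 4.95% | 3.8% | 1.2% |
| 220 | 20% vs 12% (assumed; not in the documents) | 62.7% | 58.3% | 4.5% |

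The reverse conflict had probability zero to five decimals.

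**The case against.** The strongest reply is that the decision is already fixed. The SAP gives the test one role and the odds ratio and interval another, as measures of association and precision. Nothing lets the interval override the test. This stands. A reader might infer that the choice between test and interval would be made after seeing the data, or that type I error is at risk. The documents do not support either, because the Wald test is named in advance as the decision test.

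A reader might also infer that exact conditioning would collapse because age and cPRA are continuous. The SAP does not state the form in which either enters the model. A small enumeration (20 subjects, 6 events, 30 replicates) gave a degenerate reference set in 100% of replicates with a truly continuous covariate, 27% with integer age plus integer cPRA, and 0% with integer age alone. It does not carry over to trial size, and the point does not need it.

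Third, the conflict rates come from unadjusted tables and the worked example is a chosen borderline case. That stands too: the rates show that such conflicts can occur, and are not this model's risk.

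Finally, the word may simply be a slip. The protocol does not require an exact interval, and the SAP also reports the difference in proportions with a 95% CI. That may well explain how the wording arose, but the current SAP text still specifies an interval that its model does not supply.

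**Conclusion.** The point holds in a limited form. The interval specified for the primary odds ratio cannot be obtained from the specified model. If it is taken from another model, it may disagree with the p-value beside it when the result is close to 0.05. In the unadjusted illustration at the plan's 20% versus 10%, this happens in 2.9% of trials at 220 per arm and 1.8% at 275, always with a significant Wald test and an exact interval that covers 1. The rate for the adjusted mixed model is unknown.

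The conclusion rests on reading *exact* in its standard conditional sense and on site staying in the model as a random effect. The decision rule, the type I error and the sample size are unaffected. It is a reporting fault in the headline estimate and should be corrected. It carries over wherever the same analysis is reused, namely the FAS and PPS analyses.

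**What to change.** In SAP 7.4.1.1, delete the word exact and state that the treatment odds ratio is reported with its 95% Wald CI from the same fitted mixed logistic model. Name the procedure and the estimation method, and use the same reference distribution for the interval as for the 1-df Wald chi-square. The agreement depends on this: a normal-based Wald interval matches the chi-square test by construction, whereas a t-based mixed-model interval could differ slightly from it.

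If an exact analysis is wanted, list it separately as a stratified sensitivity analysis, with its strata named and no role in the decision. It would also help to say whether age and cPRA enter as continuous or categorised.

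The cost is one or two sentences in the SAP before database hard lock. No data collection, sample size or decision rule changes.
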